11.2.2 Efficacy Analysis

All efficacy analyses will be conducted using the FAS, unless otherwise specified.

In order to satisfy the primary endpoint requirements of different regulatory agencies, 2 primary efficacy endpoints will be evaluated. Two separate SAPs will be developed to describe the statistical methodology for the analysis of each primary efficacy endpoint. In the first SAP, the endpoint described as "Primary Efficacy Endpoint" in Section 3.1 will be assessed as the primary efficacy endpoint, and the endpoint described as the "Alternative Primary Efficacy Endpoint" in Section 3.2 will be assessed as the first secondary efficacy endpoint. In the second SAP, the endpoint described as "Alternative Primary Efficacy Endpoint" in Section 3.2 will be assessed as the primary efficacy endpoint, and the endpoint described as the "Primary Efficacy Endpoint" in Section 3.1 will be

assessed as the first secondary efficacy endpoint. Both SAPs will evaluate the additional secondary efficacy endpoints described in Section 3.3.

For the efficacy evaluation of the platelet count responses, platelet counts assessed by local labs will be used. Platelet counts collected via the central lab will be used in the safety assessments of clinical laboratory tests.

Primary Efficacy Endpoint:

The primary efficacy endpoint is the durable platelet response as defined by the proportion of subjects achieving at least 6 out of 8 weekly platelet counts $\geq 50 \times 10^9 / L$ during the last 8 weeks of the 12 week Treatment Period in the Core Phase, in the absence of rescue medication. The null hypothesis is that the treatment effect of avatrombopag is the same as that of placebo. The alternative hypothesis is that the treatment effect of avatrombopag is different than that of placebo.

The primary efficacy endpoint will be tested between avatrombopag and placebo using the Cochran-Mantel-Haenszel 2-sided test at α =0.05, adjusting for age cohort and Baseline platelet count (\leq 15×10⁹/L vs >15×10⁹/L), or the Fisher's exact test, when data is sparse. In addition, the numbers and percentages of responders in each treatment group, the associated 95% confidence intervals (CI), and the 95% CI for the difference between avatrombopag and placebo will be summarized. The primary analysis will be performed based on the FAS and repeated on the PPS as a supportive analysis. Other sensitivity analyses of the primary efficacy endpoint may be performed as appropriate.

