11.2.2.1 Secondary Efficacy Analysis

The secondary efficacy endpoints for this study are:

- The percentage of weeks subjects have a platelet count $\geq 50 \times 10^9 / L$ during 12 weeks of treatment in the Core Phase, in the absence of rescue therapy.
- Platelet response at Day 8 (defined by the proportion of subjects with a platelet count $\geq 50 \times 10^9 / L$ at Day 8, in the absence of rescue therapy).
- The percentage of weeks subjects have a platelet count between $\geq 50 \times 10^9 / L$ and $\leq 150 \times 10^9 / L$, during 12 weeks of treatment in the Core Phase, in the absence of rescue therapy.
- The proportion of subjects who require rescue medications during 12 weeks of treatment in the Core Phase of the study.
- Incidence and severity of bleeding symptoms associated with ITP measured using the WHO Bleeding Scale.

The categorical variables (e.g., proportion) will be summarized and analyzed in the same manner as the primary efficacy endpoint. The continuous variables (e.g., percentage of weeks subjects have a platelet count $\geq 50 \times 10^9 / L$) will be analyzed using nonparametric Wilcoxon Rank Sum tests.

If the test of the treatment effect on the primary efficacy endpoint is statistically significant, the statistical tests on the secondary efficacy endpoints will be considered inferential; otherwise, the tests will be considered descriptive and no statistical inference can be drawn with regard to the secondary efficacy endpoints.

To control the family-wise Type I error rate at a significance level of α = 0.05 (2-sided), a step-down closed testing procedure will be used when testing the secondary efficacy endpoints. Starting with the first secondary efficacy endpoint, if the test is significant at α = 0.05, then the test on the next endpoint will be considered inferential; otherwise, the tests on the subsequent endpoints will be considered descriptive only. This process will be repeated from the top of the hierarchy for the remaining endpoints. The hierarchy of the closed testing will be defined in the SAPs.

The efficacy variables collected during the Extension Phase will be summarized descriptively. Additional efficacy analyses will be performed if deemed necessary. The details of the analyses will be described in the SAP that will be finalized prior to database lock.

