2. STUDY DESIGN

2.1 Summary of Study Design

AVA-PED-301 is a multi-center, randomized, double-blind, placebo-controlled, parallel-group study in pediatric subjects with a 12 week Core Phase followed by a 2-year open-label Extension Phase to evaluate the efficacy, safety, tolerability, and PK/PD profile of avatrombopag, as well as to provide data on palatability/acceptability, dosing parameters, and response to treatment.

The study will enroll at least 72 pediatric subjects, aged ≥ 1 to <18 years (Figure 1). Subjects will be assigned to 3 age cohorts in a 2:2:1 ratio and subjects will be randomized within each cohort in a 3:1 ratio to receive either avatrombopag or placebo. Subject age at the time of randomization will be used. Cohort 1 and Cohort 2 will each enroll more subjects than will be enrolled in Cohort 3 in order to minimize the exposure of the youngest age group to placebo. Randomization will be stratified by age cohort. Subjects will also be stratified by an average baseline platelet count of $\leq 15 \times 10^9/L$ or $>15 \times 10^9/L$ to $<30 \times 10^9/L$ in order to ensure treatment groups are approximately balanced.

[figure not shown]
Enrollment into the Core Phase will be staggered by descending age cohort.

- Cohort 1: \ge 12 to \le 18 years (n = 21 avatrombopag; 7 placebo)
- Cohort 2: \geq 6 to <12 years (n = 21 avatrombopag; 7 placebo)
- Cohort 3: ≥ 1 to ≤ 6 years (n = 12 avatrombopag; 4 placebo)

All available PK and safety data through Week 10 of the Core Phase will be reviewed by the Sponsor and/or the Sponsor's designee (e.g., for unblinded PK data) for the first 10 subjects enrolled into Cohort 1 prior to opening enrollment into the Core Phase for subjects in Cohort 2. Likewise, all available PK and safety data through Week 10 will be reviewed by the Sponsor and/or the Sponsor's designee (e.g., for unblinded PK data) for the first 10 subjects enrolled into Cohort 2, prior to opening enrollment into the Core Phase for Cohort 3. As the study progresses and more data become available, the PK/PD model will be updated with emerging data in order to confirm the appropriate dose of avatrombopag in each cohort. Enrollment will not stop in the current cohort for the data review after Week 10, or for the data review after each cohort is fully enrolled. The dose of avatrombopag may be modified during the study based on results of the PK and safety data

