2.2 Sample Size Determination

The proposed sample size is based on the anticipated response rates for avatrombopag and placebo for the primary endpoint (durable response) and the key secondary endpoint (platelet response for 2 consecutive weeks).

Based on the eltrombopag PETIT2 study conducted in pediatric patients with chronic ITP, the durable response rates were 41.3% and 3.4% for eltrombopag and placebo, respectively (Grainger, 2015). It is reasonable to assume that the treatment effect of avatrombopag will be very similar to that of eltrombopag, due to both drugs being in the same class, having similar mechanisms of action, and treating similar patient populations (e.g., patients aged ≥ 1 to <18 years with relapsed or refractory disease after 1 or more previous treatments for ITP and a Baseline platelet count $<30\times10^9$ /L). With the 3:1 ratio of avatrombopag to placebo, a total of 72 subjects (54 avatrombopag and 18 placebo) will provide at least 90% power to detect a treatment difference of 37.9% in durable response at α =0.05, based on the Fisher's exact test.

In addition, a 12 week study of romiplostim in treating pediatric ITP patients showed that 88% of romiplostim treated subjects achieved a platelet count $\geq 50 \times 10^9 / L$ for 2 consecutive weeks (key secondary endpoint), whereas none of the placebo treated subjects achieved the same endpoint (Bussel, 2011). With the 3:1 ratio of avatrombopag to placebo, a total of 72 subjects (54 avatrombopag and 18 placebo) will provide $\geq 99\%$ power to detect a treatment difference of 80% in proportion of subjects achieving a platelet count $\geq 50 \times 10^9 / L$ for 2 consecutive weeks at $\alpha = 0.05$, based on the Fisher's exact test.

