7.1 General Statistical Procedures

Categorical variables will be summarized with number and percentage of subjects with a response in the category. Percentages will be based on number of subjects in the given population as noted. Number of subjects with missing information will also be included. Percentages will be reported to one decimal place.

A 2-sided 95% exact binomial (Clopper-Pearson) confidence interval (CI) for categorical variables without multiplicity adjustment will be provided where appropriate for efficacy analysis.

Continuous variables will be summarized with number of subjects (n), mean, standard deviation (SD), median, minimum (min) and maximum (max). Mean and median will be reported to 1 more decimal place than the raw data, while the SD will be reported to 2 more decimal places than the raw data. Minimum and maximum will be reported with the same number of decimals as the original data.

Unless otherwise stated, statistical summaries will be performed for each study phase (Core Phase and Extension Phase). Core Phase analysis will be performed by treatment for each cohort and overall. Open Label Extension Phase analysis will be performed by cohort and overall.

Data that is not summarized will be listed only. Unless otherwise specified in the text, all listings will be provided for the Full Analysis Set and will be ordered by subject number, study phase (Core Phase and Extension Phase) and visit and repeated by cohort for available data.

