7.4 Efficacy Analysis

Unless otherwise stated, all primary and secondary efficacy endpoints defined in Section 3.2.1 will be analyzed for the FAS and PPS.

For the efficacy evaluation of the platelet count responses, platelet counts assessed by local labs will be used. Platelet counts collected via the central lab will be used in the safety assessments of

clinical laboratory tests.

The methods used for efficacy analysis for the Core Phase are summarized in Error! Reference source not found.3. All Cochran-Mantel-Haenzel (CMH) tests at alpha=0.05 within each age cohort will be performed adjusting for baseline platelet count category ($\leq 15 \times 10^9 / L \text{ vs} > 15 \times 10^9 / L$). For the CMH test in the overall group, the test will be performed adjusting for age cohort and baseline platelet count category. Fisher's exact test will be used if the number of durable platelet responders is spare in the strata (less than 3 in a specific subgroup). Durable platelet response with 2-sided 95% exact binomial (Clopper-Pearson) confidence interval (CI) will be provided. The difference in response rate (avatrombopag – placebo) with 2-sided 95% CI (Wald) will also be provided.

Subjects without sufficient data for the determination of response status (i.e., responder versus non-responder) will be treated as non-responders in the analysis.

For the primary efficacy endpoint determination, a subject must have remained in the Core phase through at least Week 10 (to have at least 6 weeks of platelet count data starting from week 5 to either week 12 if the subject completes the core phase or the last week if the subject prematurely terminates the core phase). If a subject terminates the Core phase prior to Week 10, they would be considered a non-responder for the primary efficacy endpoint.

Endpoint	Analysis Method
Primary Efficacy Endpoint	
Durable platelet response defined as proportion of subjects achieving at least 6 out of 8 weekly platelet counts $\geq 50 \times 10^9 / L$ during the last 8 weeks of the 12 week treatment period in the Core Phase in the absence of rescue medication. In the case of rescue medication being used, platelet count assessments from the start date of rescue medication up until 4 weeks after the end date of rescue medication will be excluded from analysis.	CMH test

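### The Wald 95% CI for the response-rate difference is unsuited to placebo groups of 18, 7, 7 and 4 with almost no expected responders; use a score interval

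*SAP*

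**What the plan says.** SAP 7.4 gives the durable response rate a Clopper-Pearson interval in each arm and the difference an interval "with 2-sided 95% CI (Wald) will also be provided". It foresees sparse data for the test: Fisher's exact test replaces CMH when the number of durable responders "is spare in the strata (less than 3 in a specific subgroup"), and a note under the efficacy table repeats the fallback for a CMH test that fails. There is no such fallback for the interval.

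Protocol 11.2.2 asks, for both the primary and the alternative primary endpoint, that "the 95% CI for the difference between avatrombopag and placebo will be summarized". It names no method, so Wald is the SAP's own choice.

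SAP 2.1 plans 54 avatrombopag and 18 placebo children: 21 and 7 in each of Cohorts 1 and 2, and "n = 12 avatrombopag; 4 placebo" in Cohort 3. SAP 7.1 states that "Core Phase analysis will be performed by treatment for each cohort and overall". SAP 2.2 plans on a cited study in which "durable response rates were 41.3% and 3.4% for eltrombopag and placebo, respectively". For "the key secondary endpoint (platelet response for 2 consecutive weeks") it cites 88% on active treatment and none on placebo, and states power for a difference of 80 percentage points.

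**The concern.** The Wald standard error estimates each arm's variance from its observed proportion. With no placebo responder the placebo term is zero, and the interval acts as if the placebo rate were known to be 0%. The placebo uncertainty shown by the Clopper-Pearson interval in the same output then never reaches the difference. At the planning rates this pushes the lower limit up, in favour of the drug.

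At stake is the reported precision of the effect size, overall and by age cohort. The CMH or Fisher test, the testing hierarchy and the type I error are untouched.

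**Working it through.** **Inputs.** Sizes 54/18, 21/7 and 12/4 (SAP 2.1). Durable response 41.3% against 3.4%; two consecutive counts 88% or 80% against 0% (SAP 2.2). Rates of 20% against 3.4%, and any placebo rate above 0% for two consecutive counts, are assumptions.

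**The plan's own figure.** Full enumeration of both binomials with the two-sided Fisher test at 0.05, 54/18, 41.3% against 3.4%, gives power of 94.5%. The stated figure of at least 90% is reproduced.

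**Chance of no placebo responder at 3.4%.** 0.966^18 = 0.537; 0.966^7 = 0.785; 0.966^4 = 0.871. The Clopper-Pearson upper limit after zero responders is 1 − 0.025^(1/m): 18.5% for 0/18, 41.0% for 0/7 and 60.2% for 0/4.

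**Formulas.** Wald: d ± 1.96 × √[p(1−p)/n + q(1−q)/m]. Miettinen-Nurminen (MN): all differences δ for which |d − δ| ≤ 1.96 × √{[N/(N−1)] × [p̃(1−p̃)/n + q̃(1−q̃)/m]}, where p̃ and q̃ are the maximum-likelihood rates under p̃ − q̃ = δ and N = n + m. Both are unstratified.

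**Worked example, 22/54 against 0/18.** d = 0.407. Wald SE = √[0.407 × 0.593/54 + 0] = 0.0669, so the half-width is 0.131 and the interval 27.6 to 53.8%. MN gives 21.5 to 54.1%.

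**Other examples.**
- 9/21 against 0/7: Wald 21.7 to 64.0%, MN 2.8 to 63.8%.
- 5/12 against 0/4: Wald 13.8 to 69.6%, MN −15.2 to 68.8%, Fisher p = 0.24.
- 12/12 against 0/4: Wald 100 to 100%, MN 49.4 to 100%.

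**Exact coverage, durable response at 41.3% against 3.4%** (all outcomes enumerated)

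| | 54/18 | 21/7 | 12/4 |
|---|---|---|---|
| Wald coverage | 93.8% | 93.4% | 87.5% |
| MN coverage | 96.6% | 97.2% | 97.5% |
| Wald wholly above truth (nominal 2.5%) | 4.2% | 3.6% | 6.0% |
| Wald wholly below truth | 2.0% | 3.0% | 6.5% |
| Wald wholly above truth, given no placebo responder | 7.6% | 4.6% | 6.9% |
| Mean Wald lower limit minus mean MN lower limit (points) | 6 | 17 | 27 |

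**Smaller effect, 20% against 3.4% (assumed).** Wald covers 95.3%, 91.7% and 92.1%.

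**Two consecutive counts.** At 88% against 0%, Wald covers 89.2%, 92.3% and 77.5%; MN 97.6%, 96.7% and 95.4%. At 80% against 0%, Wald covers 92.0%, 92.8% and 91.2%; MN 96.9%, 95.7% and 98.1%. At a true placebo rate of exactly 0% the zero placebo variance is correct, so this shortfall comes from the high avatrombopag rate. If the placebo rate is instead assumed to be 5%, overall Wald coverage at 88% falls to 85.2%. The Wald upper limit exceeds 100% in 36% (80% against 0%) to 69% (88% against 0%) of 21/7 cohorts and in 49% to 62% of 12/4 cohorts. For durable response this almost never happens (at most 0.4%, at 12/4). The zero-width interval occurs in 0.88^12 = 22% of 12/4 cohorts at 88% against 0%.

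**Agreement with Fisher at the durable planning rates.** The interval excludes 0 while Fisher p > 0.05 in 4%, 54% and 80% of cases for Wald, and in 1%, 14% and 14% for MN. This matters only if the fallback test is used. If the threshold of fewer than 3 responders is read per arm, which is an assumption, the placebo arm meets it in 97.8% of trials overall and in more than 99.8% of groups of 7 or 4.

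**The case against.** Four points can be made for leaving the text alone.

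- **Direction.** In Cohort 3 about half the Wald misses are upper limits that are too low (6.5% against 6.0%). At the assumed 20% against 3.4% in 12/4, Wald lies above the truth only 1.9% of the time even given 0/4. This stands: the upward error in the lower limit is a statement about the planning rates, not about every scenario. At the planning rates, given no placebo responder, it holds at all three sizes.
- **Benchmark.** MN is itself conservative at the lower limit: it lies wholly above the truth at most 0.7% of the time in every scenario checked. The 6, 17 and 27 points are therefore distances from a cautious interval, not the size of Wald's error. For the overall primary result Wald is 1.2 points under nominal and MN 1.6 over. This also stands; MN's advantage there is that it errs on the safe side.
- **Scope.** The most striking figures concern two consecutive counts, while the Wald sentence follows one on durable response. Extending it is an inference, though a supported one: Protocol 11.2.2 asks for this interval on that endpoint too, and 11.2.2.1 says "The categorical variables (e.g., proportion) will be summarized and analyzed in the same manner as the primary efficacy endpoint".
- **Weight.** Nothing is decided by this interval, and the arm-level exact intervals partly disclose the placebo uncertainty. That limits the importance of the point. It does not justify an interval that can have zero width with 16 children.

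The Newcombe interval would also serve (coverage 96.3% overall and 95.8% in Cohort 3 at the durable planning rates). That is a reason to choose among score-type intervals, not to keep Wald.

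**Conclusion.** The concern holds, as a reporting correction worth considering. For durable response the under-coverage is modest overall and in Cohorts 1 and 2, and clear in Cohort 3. For two consecutive counts it is larger, if the Wald sentence applies there. The overall conclusion on the primary endpoint would not change at the planning rates, because both lower limits in the 54/18 example are far above zero. In Cohort 3 the two methods can give different impressions, as 5/12 against 0/4 shows. The figures assume the planned group sizes, the cited rates and unstratified intervals. The responder counts are illustrations, not trial data.

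**What to change.** In SAP 7.4, replace Wald with the Miettinen-Nurminen score interval, unstratified, for all response-rate differences, overall and by cohort. State in the same sentence that it applies to the primary and to the categorical secondary endpoints, so that its scope no longer has to be inferred. Make the change before unblinding, so that a degenerate Wald interval does not force a post hoc switch.

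The cost is one SAP phrase and one software option. No protocol amendment is needed. The intervals widen: at the durable planning rates the mean width is 35.5 instead of 30.3 percentage points overall, 62 instead of 47 at 21/7, and 84 instead of 59 at 12/4. Disagreement with Fisher can still occur at the margin: 11/54 against 0/18 gives 1.7 to 33.0% with p = 0.055.

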3.2 Study Endpoints

3.2.1 Efficacy Endpoints

• Primary Efficacy Endpoint

Durable platelet response defined as the proportion of subjects achieving at least 6 out of 8 weekly platelet counts ≥50×10⁹/L during the last 8 weeks of the 12 week Treatment Period in the Core Phase in the absence of rescue medication

• Alternative Primary Efficacy Endpoint (per EMA PIP)

Platelet response as defined by the proportion of subjects for whom at least 2 consecutive platelet assessments are ≥50×10⁹/L over the 12 week Treatment Period in the Core Phase in the absence of rescue medication

Additional Secondary Efficacy Endpoints

- The percentage of weeks subjects have a platelet count ≥50×10⁹/L during 12 weeks of treatment in the Core Phase, in the absence of rescue therapy.
- Platelet response at Day 8 (defined by the proportion of subjects with a platelet count $\geq 50 \times 10^9$ /L at Day 8, in the absence of rescue therapy).
- The percentage of weeks subjects have a platelet count between ≥50×10⁹/L and ≤150×10⁹/L, during 12 weeks of treatment in the Core Phase, in the absence of rescue therapy.
- The proportion of subjects who require rescue medications during 12 weeks of treatment in the Core Phase of the study.
- Incidence and severity of bleeding symptoms associated with ITP measured using the WHO Bleeding Scale

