4.5 Handling Rules for Platelet Counts

Platelet counts are collected at local laboratories for eligibility and efficacy assessments. Platelet count is also included in the hematology panel sent to the central laboratory as a safety evaluation. For the efficacy analyses, only platelet counts assessed by the local laboratories will be included in

the calculations and summaries. For the safety analyses, only platelet counts assessed by the central laboratory will be included in the summaries.

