Alternative Primary Efficacy Endpoint • Platelet response defined as proportion of subjects for whom at least 2 consecutive platelet assessments are ≥50×10 ⁹ /L during last 8 weeks of the 12 week treatment in the Core Phase in the absence of rescue medication	CMH test

Secondary Efficacy Endpoints

Percentage of weeks subjects have a platelet count $\geq 50 \times 10^9 / L$ during 12 weeks of treatment in the Core Phase, in the absence of rescue therapy. Denominator for this calculation is based on the number of weeks the subject was on treatment (up to 12 weeks)

CMH test

tests

Nonparametric

Wilcoxon Rank Sum

Platelet response at Day 8 (defined by the proportion of subjects with a platelet count $\geq 50 \times 10^9 / L$ at Day 8, in the absence of rescue therapy)

Endpoint	Analysis Method
• Percentage of weeks subjects have a platelet count between ≥50×10 ⁹ /L and ≤150×10 ⁹ /L, during 12 weeks of treatment in the Core Phase, in the absence of rescue therapy. Denominator for this calculation is based on the number of weeks the subject was on treatment (up to 12 weeks)	Nonparametric Wilcoxon Rank Sum tests
• Proportion of subjects who require rescue medications during 12 weeks of treatment in the Core Phase of the study	CMH test
• Overall incidence and incidence of severe bleeding symptoms (scale 3 and 4) associated with ITP measured using the WHO Bleeding Scale	CMH test
Exploratory Efficacy Endpoint	
• Month 3 durable platelet response defined as the proportion of subjects achieving at least 3 out of 4 weekly platelet counts ≥50×10 ⁹ /L during the last 4 weeks of the 12 week Treatment Period in the Core Phase in the absence of rescue medication	CMH test

Note: Fisher's exact test will be used if CMH test fails.

If the test of the treatment effect on the primary efficacy endpoint is statistically significant, the statistical tests on the secondary efficacy endpoints will be considered inferential; otherwise, the tests will be considered descriptive and no statistical inference can be drawn with regards to the secondary efficacy endpoints.

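### The four-week post-rescue exclusion is written for the primary endpoint only, so the handling of post-rescue counts in the other platelet endpoints is left open

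*SAP*

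**What the plan says.** SAP 7.4 (Table 3) gives each efficacy endpoint its own row.

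- **Primary (durable response).** The row requires absence of rescue and adds that, where rescue is used, "platelet count assessments from the start date of rescue medication up until 4 weeks after the end date of rescue medication will be excluded".
- **Alternative primary.** "Platelet response defined as proportion of subjects for whom at least 2 consecutive platelet assessments are" at or above 50×10⁹/L, "during last 8 weeks of the 12 week treatment in the Core Phase in the absence of rescue medication". No window is given.
- **Percentage of weeks (two rows).** "in the absence of rescue therapy. Denominator for this calculation is based on the number of weeks the subject was on treatment". No window is given, and nothing says what happens to weeks affected by rescue.
- **Day 8 response.** "at Day 8, in the absence of rescue therapy". No window is given.
- **Month 3 durable response (exploratory).** "during the last 4 weeks of the 12 week Treatment Period in the Core Phase in the absence of rescue medication". No window is given.

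No general rule fills the gap. SAP 4.5, on handling platelet counts, deals only with the choice of laboratory: "For the efficacy analyses, only platelet counts assessed by the local laboratories will be included in" the efficacy calculations. Protocol 8.6 defines rescue and its recording without an analysis window, and Protocol 11.2.2 and 11.2.2.1 give none either. The SAP's rule for insufficient data (non-responder) does not mention rescue.

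**The concern.** Protocol 8.6 allows rescue when platelets must be raised urgently, and lists corticosteroids, IVIg, anti-D and platelet transfusion. A count taken soon afterwards may reflect the rescue and not the study drug. The sponsor accepted this for the primary endpoint by discarding counts for four weeks after rescue ends.

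The other endpoints are built on the same weekly local counts. A programmer working down Table 3 has a natural basis for applying the window to the primary row alone. One platelet count could then be excluded from the primary and counted as response in the key secondary. Rescued children can stay in the Core Phase and contribute such counts, because removal for repeated or prolonged rescue is optional (Protocol 5.3).

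At stake are the estimates for the key secondary, which heads the testing hierarchy in this SAP, the two percentage-of-weeks endpoints and Month 3 response.

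**Working it through.** **1. The plan's own figures.** SAP 2.2 plans 54 v 18 subjects with Fisher's exact test at α = 0.05; the protocol's tests are two-sided. Summing the binomial probabilities of all outcomes with two-sided p ≤ 0.05 gives 94.5% power for 41.3% v 3.4% (stated: at least 90%) and above 99.9% for 80% v 0% (stated: at least 99%). Both reproduce. Neither uses a rescue rate, so neither changes here.

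**2. Does requiring absence of rescue settle the matter?** Test it on the primary row, which has both that requirement and the window. Weekly counts fall on Days 8, 15, …, 85; Weeks 5 to 12 are Days 36 to 85. For a one-day rescue on Day d, counts from Day d to Day d + 28 are excluded.

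| Rescue day | Counts left of the 8 | Can the child still reach 6? |
|---|---|---|
| 2–7 | 8 | yes |
| 8–14 | 7 | yes |
| 15–21 | 6 | yes |
| 22–71 | 3 to 5 | no |
| 72–78 | 6 | yes |
| 79–85 | 7 | yes |

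A rescued child can therefore still be a durable responder. In the primary row, absence of rescue cannot mean that any rescue is failure, and the window sentence does the work. In the other rows the same requirement has at least three readings: any rescue is non-response; only counts during rescue are barred; or the four-week window applies.

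**3. Exposure if only counts during rescue are barred.**

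- *Alternative primary:* a one-day rescue with its window inside the Core Phase is followed by 4 weekly counts within 28 days. Two consecutive counts suffice.
- *Percentage of weeks:* at most 4 of 12 weeks, or 33 points for that child, and only if all four counts qualify.
- *Month 3:* 3 of 4 counts are needed on Days 64 to 85. A one-day rescue on Days 57 to 63 has all four inside its window.
- *Day 8:* only rescue in the first week matters.

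**4. Illustrative size for the alternative primary.** The documents give neither a rescue rate nor a post-rescue response rate; all rates below are assumptions. Placebo starts from the planning value of 0%.

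Spurious placebo response = rescue rate × proportion of rescued children with two consecutive qualifying counts:

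- low: 0.20 × 0.30 = 6% (0.06 × 18 = 1.1 children)
- high: 0.40 × 0.60 = 24% (0.24 × 18 = 4.3 children)

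Fisher power for 80% v 24% is 99.1%. That calculation sets carry-over on avatrombopag to zero. If avatrombopag rescue is half the placebo rate (20%) with the same 60%:

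- rescue spread evenly: 80% + 20% × 0.20 × 0.60 = 82.4%, difference 82.4 − 24 = 58.4 points
- all rescue among non-responders: 80% + 0.20 × 0.60 = 92%, difference 92 − 24 = 68 points

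Against a true 80 points, the loss is 24, 21.6 or 12 points.

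A wider grid takes placebo rescue 20% to 60%, avatrombopag rescue half of that, spread evenly, and carry-over 25% to 75%. It runs from 80.5% v 5% (75.5 points, power above 99.9%) to 84.5% v 45% (39.5 points, power 86%).

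**The case against.** The strongest reply is that each of these rows does require absence of rescue. A reader might infer that the SAP allows rescue-driven counts to be scored as response. The documents do not support that: no row credits such counts, and a strict reading bars them. This stands. What can be shown is an unsettled rule, which a row-by-row reading would resolve in the lenient direction.

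A reader might also infer that the main endpoint for the European regulator is compromised. The protocol (Section 3) makes the alternative endpoint primary only in a second SAP, which was not supplied, and its rescue handling is unknown. In this SAP the endpoint is the key secondary.

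A loss of 24 points might be taken as the expected damage. It rests on assumed rates and ignores carry-over on avatrombopag, which would offset part of it. Nothing in the documents shows that rescue falls mainly on placebo. If it does, the bias runs against avatrombopag and creates no false claim of superiority.

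None of this removes the gap. The primary row has the same requirement and still needed the window, and no general rule extends it.

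**Conclusion.** The point holds as a gap in the rescue rule: the window is defined for the primary endpoint and not for the other platelet endpoints derived from the same counts. The primary analysis and the stated power are unaffected.

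The alternative primary is most exposed, then percentage of weeks and Month 3; Day 8 is affected least. The size cannot be derived from the documents. Under the assumed rates, the difference on the alternative primary is diluted if rescue is commoner on placebo. Power stays near 99% in the 80% v 24% illustration and falls to 86% only at the extreme of the wider grid. The main harm is to the estimate and to consistency between endpoints. Because the repair is specific and cheap, it should be made.

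**What to change.** Before unblinding, move the existing exclusion sentence out of the primary row into a general rule in SAP 7.4 that covers every Core Phase platelet-count efficacy endpoint: primary, alternative primary, both percentage-of-weeks endpoints, Day 8 and Month 3.

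State also whether excluded weeks stay in the percentage-of-weeks denominator, which is now weeks on treatment. Keeping them there as not in range and removing them from numerator and denominator are both coherent; the SAP should name one. If the sponsor prefers to treat any rescue as non-response for a binary endpoint, writing that down would also close the gap. The second SAP should be checked for the same rule.

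In the same edit, reconcile the alternative primary's assessment period, a separate inconsistency: SAP 3.2.1 has "over the 12 week Treatment Period in the Core Phase in the absence of rescue medication", while Table 3 restricts it to the last 8 weeks.

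The cost is SAP wording and the matching derivation code. No data collection, sample size or trial conduct changes.
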